TYRO Champion Dads

Statistical Analysis Plan

12/9/2024

Clinicaltrial.gov ID:
NCT05256992

1. Data Analysis

Briefly describe the planned approach for data analysis. If an impact analysis is proposed, name the key dependent and independent variables, and describe any methods to minimize Type I error (i.e., finding positive impacts by chance) such as limiting the number of impacts to be analyzed and/or multiple comparison correction. Describe proposed approach(es) for addressing missing data.

Identify impact study sample

The impact study sample includes participants who: 1) were eligible to be randomized based, 2) gave recorded informed consent to be part of the study and randomly assigned to a treatment group, and 3) took both an entrance and exit and/or follow-up survey. The CONSORT diagram in Appendix A shows exclusion criteria and the anticipated size of the overall impact study sample, which we anticipate to differ for attitudinal items that will use wave 2 data vs behavioral questions that will use wave 3 data. The analytic sample for particular outcome measures will vary based on missing data.

Defining analysis measures

For each outcome construct, we have identified the relevant measures from nFORM that are theoretically aligned with that construct. We will generate a correlation matrix between items in a given construct to ensure that theoretically related items are also empirically related in our data set. Items that are not strongly correlated with other items in a construct will be removed as necessary. Factor analysis will be used to ensure that all construct items hang together (using an alpha of 0.7 or higher as the threshold).

Once we are confident that all of the items align with a given construct, we will create a composite measure by taking an average of the scores on each non-missing item in the construct. The measure definition matrix below provides information on each proposed outcome measure.

For the sake of consistency and simplicity, parenting and co-parenting analyses will use a participant's youngest child as the focal child.

Measure	Sample	Variable Type	Data source(s)	Variable Name	Definition
Co-parenting relationship behaviors	Has at least one child age 24 or younger	Continuous (range from 1 to 5 where 1 is strongly disagree and 5 is strongly agree)	nFORM entrance, OLLE follow-up	Copar_Beh	Average of 11 survey items that relate to positive interactions with the mother of participant's youngest child

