Parenting relationship behaviors	Has at least one child age 24 or younger, saw child within past month	Continuous (range from 1 to 5 where 1 is never and 5 is every day or almost every day)	nFORM entrance, OLLE follow-up	Par_Beh	Average of 10 to 11 survey items (depending on child age) that relate to frequency of positive interactions with participant's youngest child
Parenting relationship attitudes	Has at least one child age 24 or younger, saw child within past month	Continuous (range from 1 to 5 where 1 is always and 5 is never)	nFORM entrance, nFORM exit	Par_Att	Average of 6 survey items that relate to frequency of feelings about participant's youngest child
Parenting relationship behaviors	Has at least one child age 24 or younger, saw child within past month	Continuous (range from 1 to 5 where 1 is never and 5 is every day or almost every day)	nFORM entrance, OLLE follow-up	Parent_Fight	Reported frequency of fighting with child
Partner relationship behaviors	All survey respondents	Continuous (range from 1 to 5 where 1 is never and 5 is always)	OLLE pre-survey, OLLE post-survey, OLLE follow-up	Partner_Fight	Reported frequency of fighting with partner
Partner relationship behaviors	All survey respondents	Continuous (range from 1 to 5 where 1 is never and 5 is always)	OLLE pre-survey, OLLE post-survey, OLLE follow-up	Partner_Disagree	Average of 7 survey items related to frequency of disagreement with partner on different topics

Analytic approach

The main goal of this impact study is to assess the impact of the addition of the Ray of Hope curriculum intervention on participant attitudinal outcomes immediately following program completion, and behavioral outcomes six months after program enrollment, as compared to the impact of standard TCD services alone.

Participation benefits are defined by the primary and secondary outcomes presented earlier in the theory of change logic model and with research questions and hypotheses. Impact estimates are based on participant responses to the OLLE Follow-up Survey across randomly assigned study groups to compare primary and secondary outcomes between them 6-months after TCD Project enrollment. More positive outcomes for the treatment group will be attributed to the intervention given that other TCD services are delivered in the same ways to both study groups under a shared condition.

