Steps begin by creating constructs that serve as the dependent variables used to model comparisons of primary outcomes—parent, co-parent, and partner relationship behaviors—and secondary outcomes—parenting attitudes. Constructs are comprised of the relevant survey items on the nFORM Community Fathers Survey and the OLLE Survey. Constructs are confirmed with psychometric evidence derived from confirmatory factor analysis (CFA), except when they are already supported by evidence of reliability and validity or based on one item that is sufficiently broad to investigate an outcome. Next, results from baseline equivalency analyses identify co-variates to specify in the model that control for any detected differences in participant characteristics or developmental starting points in healthy family relationships and economic stability. Model results are interpreted to determine if assignment to the treatment group positively predicts ($p < .05$) more improved outcomes than the control group 6-months after enrollment into TCD services for behavior outcomes and immediately following program completion for attitudinal outcomes.

Finally, type 1 and type 2 error are controlled in this study. Type I error is the rejection of a true null hypothesis (also known as a "false positive" finding or conclusion; example: "an innocent person is convicted"). We control for type 1 error in two ways. First, alpha levels are set at .05, so only 1 in 20 findings should result in a false positive, and we plan to use the Bonferroni correction method to adjust for multiple hypothesis tests. Second, research questions are limited to modeling six outcomes. Type II error is the non-rejection of a false null hypothesis (also known as a "false negative" finding or conclusion; example: "a guilty person is not convicted"). We control for Type 2 error by having sufficient power to detect small or nearly small minimum detectable effect sizes. (The estimated effect sizes are all almost small effects that would be detected, based on best practices outlined by Cohen (1988) of small effect sizes <0.02 and medium effect sizes <0.15 .)

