Chi-Square and 2-sample t-tests assess baseline equivalency of study groups by analyzing pre-survey responses to items that describe the characteristics of participants and their developmental starting points before receiving TCD services. Participant characteristics—such as demographics, family structure, and socioeconomic background—are reported on the nFORM ACS Survey. Developmental starting points refer to the attitudes and behavior exhibited before TCD participation and are reported on the nFORM Community Fathers Entrance Survey and OLLE Pre-survey. Chi-Square tests are run for

categorical and dichotomous variables, such as relationship status (e.g., married, single, divorced) or whether a participant reports having a savings account (i.e., yes/no). Two-sample t-tests are run for interval and continuous variables, such as the number of children in a household, or levels of agreement with healthy parenting attitudes. Any differences detected across study groups are incorporated into the model as co-variates.

Study group assignment (1=treatment, 0=control) is repeatedly regressed against the dependent variables to model comparisons of outcomes constructs between study groups (see the table below). Co-variates specified in the model will control for the influence of any significant baseline differences between study groups that were detected in the baseline equivalency analyses for demographics, family structure, socioeconomic background, and developmental starting points.

Procedures to run the linear regression model rely on standard regression to model the influence of study group assignment on dependent variables. All dependent variables are continuous, such as when participants report how many hours they spend with their child or respond to multiple items in a scaled construct by indicating levels of agreement with statements about key parent attitudes.

Benefits of the Ray of Hope curriculum will confirm hypotheses if respondents assigned to the treatment group report greater improvements in outcomes ($p < .05$) than those in the control group for each outcome measure identified above.

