For the implementation analysis, program fidelity will be descriptively reported by the percentage of enrolled participants who receive: 1) any primary workshops, 2) employment supports, 3) substantive service contacts, 4) referrals. The program aims to provide all participants each of these four program components, so the percentage of participants who receive each of these will be compared to the 100% benchmark. Number of substantive service contacts per participant will also be compared to the benchmark of 8 SSCs set by OFA for FIRE grantees.

Dosage will be measured by percent of target primary workshops participants attend on average (using 90% as a benchmark), and categories of attendance (initial, halfway, 90%, 100%) will be reported and compared to targets established by the program.

Handling missing data

Outcomes

When creating the composite measures for our behavior and attitude outcomes, we will create a composite score by taking the average of multiple individual items. For these measures, our current plan is to use 20% as a threshold for allowable missing items, based on guidance from evaluation technical assistance resources. This plan is contingent on the final distribution of missing data in our data set. If participants have more than 20% of items missing for a given construct, the respondent will be assigned a missing value for that construct and will be excluded from the analytic sample for that outcome. We will not be imputing truly missing values for outcomes. To create a construct score, the average will divide by the number of non-missing values in the construct.

For outcomes that use single survey items, participants who do not respond to that item on either the pre- or follow-up survey will be excluded from the analytic sample for that outcome.

Data for the implementation outcomes could be missing as a result of programmatic data entry issues. For the sake of this evaluation, we assume that any primary or support services received by a participant are being accurately logged into nFORM, so a lack of documented attendance, service contacts, referrals, etc. is indicative of lack of services (i.e., a participant not receiving the program components as intended).

Assessing non-response bias

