We will conduct response rate analysis for each primary outcome of interest to assess non-response bias and adjust for threats to internal validity. Using data from the Applicant Characteristics Survey, we will look at demographics (race, ethnicity, age, education level) and primary reason for joining the program among participants who fall into each of the following categories: 1) non-respondents who answered no surveys after the ACS, 2) respondents who completed a pre-survey only, and 3) respondents who completed both a pre- and follow-up survey (complete case). We will also look for differential response rates between the standard/control and enhanced/treatment groups.

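### Each outcome's own baseline score enters its model only if a significance test detects an arm difference, so it is usually left out and available precision is lost

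*SAP*

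**What the plan says.** The SAP's Analytic approach gives the covariate rule three times. First, "results from baseline equivalency analyses identify co-variates to specify in the model". Then, after describing the chi-square and two-sample t-tests, "Any differences detected across study groups are incorporated into the model as co-variates". Finally, in the regression paragraph, "Co-variates specified in the model will control for the influence of any significant baseline differences between study groups that were detected". Baseline outcome scores fall under the same screen: "Developmental starting points refer to the attitudes and behavior exhibited before TCD participation", and these starting points are among the items tested. The SAP gives no significance level for the screen and no closed list of candidate variables.

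The measures table lists a baseline source for all six measures: nFORM entrance for the four parenting and co-parenting measures, and the OLLE pre-survey for the two partner measures. The model is a standard linear regression of the outcome on assignment. Success is described as more improvement in the treatment arm, but neither a change score nor a baseline-adjusted difference is defined.

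Protocol 9.3 assumes a one-tailed 0.05 test, 80% power, 620 analysed and a minimum detectable effect size of 0.2. Its row for variance explained by covariates is blank. Protocol 7.1 also frames group comparability in terms of statistically significant differences.

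**The concern.** An outcome's own baseline score is usually among its best predictors. Including it reduces residual variance whether or not the arms differ on it. Under randomisation, a test for an arm difference detects only chance imbalance and carries no information on how well a variable predicts the outcome. A screen of this kind therefore discards the baseline score in most trials and admits other variables for the wrong reason.

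Three things are at stake: power that the collected data could supply; a final model that depends on a screening level and candidate list not fixed in advance; and the meaning of improvement, which could be read as a follow-up difference, a change score or a baseline-adjusted difference.

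**Working it through.** **Inputs from the documents.** 310 per arm (Protocol 9.2 and 9.3); one-tailed 0.05, 80% power, effect 0.2 SD (Protocol 9.3); Bonferroni correction and six outcomes (SAP, Analytic approach); four outcomes in the power table (Protocol 9.3).

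**Assumptions.** Pre-post correlation r of 0.3, 0.5 or 0.6; screen at two-sided 0.05; no differential attrition.

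**1. The plan's own figure.** The unadjusted standard error is √(2/310) = 0.0803 SD. MDES = (1.645 + 0.842) × 0.0803 = 0.200. Power at 0.2 = Φ(0.2/0.0803 − 1.645) = 80.1%. The stated 0.2 therefore reproduces with covariate R² = 0.

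**2. Always adjusting.** The standard error is multiplied by √(1 − r²), and the gain is equivalent to a sample larger by the factor 1/(1 − r²).

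| r | MDES | Power at 0.2 SD | Equivalent extra participants |
|---|---|---|---|
| 0 (unadjusted) | 0.200 | 80.1% | none |
| 0.3 | 0.191 | 83.3% | 1/0.91: 10% |
| 0.5 | 0.173 | 89.1% | 1/0.75: 33% |
| 0.6 | 0.160 | 92.9% | 1/0.64: 56% |

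**3. The SAP rule.** In simulation (310 per arm, effect 0.2 SD, 20,000 trials per setting), 20 independent candidates were screened and only the own baseline score was prognostic. The number 20 is assumed, since the SAP gives no list.

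- The own baseline score entered in 4.9% to 5.2% of trials.
- At least one candidate entered in 64% to 65% of trials, as expected from 1 − 0.95^20 = 64%.
- Power at r = 0.3, 0.5 and 0.6 was 79.9%, 80.9% and 81.9% under the rule, against 83.3%, 89.3% and 93.3% when always adjusting.
- The number of candidates hardly matters: with the own baseline score as the only candidate, the rule gave 80.3%, 81.0% and 81.8%.
- With 20 candidates correlated at 0.3 (10,000 trials), it gave 80.1%, 80.6% and 81.9%.

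**4. Type I error.** With no true effect (20 candidates, 10,000 trials), the rule rejected in 5.0%, 4.4% and 4.5% of trials. There is no inflation.

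**5. With Bonferroni.**

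- At one-sided 0.05/6, power at 0.2 SD is 53.8% unadjusted, and 58.6%, 68.5% or 76.4% adjusted.
- At 0.05/4, it is 59.8% unadjusted, and 64.4%, 73.7% or 80.8% adjusted.

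**6. If improvement means a change score.** The variance is multiplied by 2(1 − r), that is 1.4, 1.0 or 0.8. Power at one-sided 0.05 is then 68%, 80% or 87%, below the baseline-adjusted figure at each r.

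**7. Fathers without a baseline score.** If a share m of fathers is dropped for this reason, the gain is cancelled when (1 − r²)/(1 − m) = 1, that is at m = r²: 9%, 25% or 36%.

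**The case against.** The SAP says that detected differences are included; it does not say that nothing else may be. Its regression paragraph also points to a table that does not follow in the available text, so a specification there cannot be wholly excluded. This limits the claim to the visible text, but three consistent statements tie covariates to detected differences. The non-response section mentions adjusting for threats to validity without naming a baseline score.

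The references to improvement, and the exclusion of single-item non-responders at the pre-survey, could suggest that a change score is intended. On that reading the baseline is always used, and the comparison with 80% no longer applies. Baseline adjustment still does better, by roughly 16, 9 and 6 points at r = 0.3, 0.5 and 0.6. The ambiguity is itself a reason to settle the model.

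The size of the gain rests on assumed correlations. Two measures are single items, and some follow-up is by telephone instead of self-entry, so r could be low; at 0.3 the gain is about three points. Using 620 for every outcome is also generous, because three measures are limited to fathers who recently saw the child. Both points stand.

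The 95% omission rate describes randomised groups. Attrition of about 30% is planned, and exit surveys mainly reach completers. If attrition produced a baseline difference of 0.1 SD (assumed), the score would enter about 24% of the time. It would still be omitted in most trials.

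**Conclusion.** The concern holds. The visible text leaves each outcome's baseline score to a significance screen that recovers almost none of the available precision. At one-sided 0.05, always adjusting adds about 3, 9 or 13 percentage points of power over the unadjusted 80% for r = 0.3, 0.5 or 0.6; the screen adds at most about 2. The gain matters more once the planned Bonferroni correction is applied, because unadjusted power at 0.2 SD is then 54% (six outcomes) or 60% (four).

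These figures depend on the assumed r, on 310 analysed per arm for every outcome and, for the screen, on a 0.05 level without differential attrition. This is an efficiency loss and an under-specified model. It is neither an error in the stated MDES nor a threat to the type I error rate. The change should be made, but the trial does not fail without it.

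**What to change.** In the SAP's Analytic approach, replace the screening rule with text to this effect: each outcome is regressed on assignment and the baseline score of the same measure in every model, whatever the baseline tests show; the treatment effect is the baseline-adjusted difference between arms, and this is what improvement means. Keep the equivalency tests as description only.

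A short list of further covariates may be fixed in advance, chosen for their expected relation to the outcome. The non-response section offers candidates: "we will look at demographics (race, ethnicity, age, education level) and primary reason for joining the program". Ethnicity may vary little, since the target population is Latino. This list is optional; the baseline score is the main part.

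Add a rule for fathers without a baseline score that is consistent with three existing statements:

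- The sample requires that fathers "took both an entrance and exit and/or follow-up survey". State whether this covers the OLLE pre-survey, the baseline source for the partner measures.
- Three measures are restricted: "Has at least one child age 24 or younger, saw child within past month". A father may meet this at follow-up but not at entrance.
- For single items, "participants who do not respond to that item on either the pre- or follow-up survey will be excluded from the analytic sample". For composites, say whether the 20% missing-item limit also applies to the baseline score.

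The cost is SAP wording, with no new data. The SAP is dated 12/9/2024 and the protocol timeline ends exit surveys on 08/01/24, so the amendment should be dated and should record whether anyone had seen outcomes by arm.

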9.3. RCTS ONLY: POWER ANALYSIS

For each confirmatory outcome, please provide power analyses demonstrating proposed sample sizes will be able to detect expected effect sizes for the outcomes targeted. Refer to previous studies of similar interventions for estimates of the required sample to inform power analyses. Note: If an impact evaluation is not proposed, this issue does not need to be addressed. You may use the table below to report the assumptions used in your power calculations, as well as the resulting minimum detectable impact for your confirmatory outcomes or provide them in the space below.

	Outcome 1	Outcome 2	Outcome 3	Outcome 4
Outcome Name	Healthier Parenting Attitudes	Healthier Partner Relationship Behavior	Healthier Parenting Behavior	Healthier Co-Parenting Behavior
Continuous or binary?	continuous	continuous	continuous	continuous

Level of significance (e.g., 0.05 percent)	0.05	0.05	0.05	0.05
Number of sides of test (one- or two-tailed)	One-tailed	One-tailed	One-tailed	One-tailed
Power (e.g., 80 percent)	80%	80%	80%	80%
Total number of individuals in analytic sample	620	620	620	620
If binary, enter mean of outcome variable				
If continuous outcome, enter the standard deviation of the outcome (>0)				
Proportion of individual-level (or within-group) variance explained by covariates				
For cluster RCTs: intraclass correlation coefficient	N/A	N/A	N/A	N/A
For cluster RCTs: proportion of group-level variance of	N/A	N/A	N/A	N/A

outcome explained by covariates				
Minimum detectable impact				
Minimum detectable effect size	0.2	0.2	0.2	0.2

If you did not provide report your assumptions using the table above, please enter them here.

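### R2 and R3 each have two outcome measures but are powered for one, and the SAP does not say how the two measures together decide the question

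*SAP*

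**What the plan says.** The Protocol asks four confirmatory outcome questions, R1 to R4 (Section 1.2), with one hypothesis each (Section 4, Hypotheses). The power table in Section 9.3 has one column per question; the R2 column, for example, is "Healthier Partner Relationship Behavior". Every column carries the same entries: "Level of significance (e.g., 0.05 percent) 0.05 0.05 0.05 0.05", "Number of sides of test (one- or two-tailed) One-tailed One-tailed One-tailed One-tailed", 80% power, a total analytic sample of 620 and a minimum detectable effect size of 0.2.

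The measure matrix (Protocol Section 10.1, repeated in the SAP) has six rows, not four:
- Partner relationship behaviors (R2): Partner_Fight, "Reported frequency of fighting with partner", and Partner_Disagree, "Average of 7 survey items related to frequency of disagreement with partner on different topics".
- Parenting relationship behaviors (R3): Par_Beh, a mean of 10 to 11 items, and Parent_Fight, "Reported frequency of fighting with child".
- One measure each for co-parenting (R4) and parenting attitudes (R1).

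The SAP's Analytic approach confirms that six outcomes are modelled, plans a Bonferroni correction without giving the number of tests or the family, and treats hypotheses as confirmed if treatment-group respondents improve more, at p < .05, "than those in the control group for each outcome measure identified above". Neither document names a lead measure for R2 or R3, combines the pair, or says what a split result means.

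**The concern.** Four outcomes are powered and six are tested, and the success rule is worded by measure while the confirmatory questions are worded by construct. For R2 and R3 the rule can be read as requiring both measures or as judging each alone, and a reader short of a rule could also accept either one. These readings have different power and different false-positive rates, and the power table describes none of them at the level of the question.

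Split results are plausible, because each pair sets a single item beside a multi-item average. If fighting with the partner improves and disagreement does not, whether R2 is confirmed depends on a reading that could be chosen after the result is known. Two of the four confirmatory questions are exposed to this.

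**Working it through.** **Inputs.** From Protocol 9.3: one-tailed alpha 0.05, 620 analysed, effect size 0.2. From Protocol 9.2: 310 analysed per arm. The SD is set to 1, because the table's SD row is blank. The correlation ρ between the two measures, scored so that higher is healthier, is not in the documents and is varied. A true effect of 0.2 SD on both measures is assumed.

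**Step 1: the plan's own figure.** The expected z statistic is 0.2 / √(2/310) = 2.490. Power = Φ(2.490 − 1.645) = Φ(0.845) = 80.1%. The stated 80% reproduces for a single test, so the table's arithmetic is sound.

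**Step 2: both measures required, uncorrected.** Power = Φ₂(0.845, 0.845; ρ), the bivariate normal probability that both z statistics exceed 1.645. At ρ = 0 this is 0.801² = 0.642.

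**Step 3: either measure enough, uncorrected.** Under the null, the chance of a false confirmation of one question is 1 − Φ₂(1.645, 1.645; ρ). At ρ = 0 this is 1 − 0.95² = 9.75%.

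**Step 4: both measures required, Bonferroni over six.** One-sided alpha is 0.05/6 = 0.00833, critical value 2.394. Per measure, Φ(2.490 − 2.394) = 53.8%. For both at ρ = 0, 0.538² = 0.290.

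| ρ | Both, uncorrected | Analysed per arm for 80% on both, uncorrected | Either, false positive, uncorrected | Both, Bonferroni over six |
|---|---|---|---|---|
| 0 | 64.2% | 420 | 9.75% | 29.0% |
| 0.3 | 66.8% | 408 | 9.3% | 33.8% |
| 0.5 | 68.9% | 396 | 8.8% | 37.2% |
| 0.7 | 71.4% | 380 | 8.0% | 41.2% |
| 0.9 | 75.1% | 352 | 6.8% | 46.7% |

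Uncorrected power for both reaches 80.1% only at ρ = 1.

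**Step 5: what Bonferroni does to the either-one rule.** With alpha a per test and non-negative correlation, the per-question false-positive rate is at most 1 − (1 − a)²:
- family of two, a = 0.025: 4.9%
- family of four, a = 0.0125: 2.5%
- family of six, a = 0.00833: 1.7%

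**Step 6: one deciding measure per question, Bonferroni over four.** The critical value at one-sided 0.0125 is 2.241. Power = Φ(2.490 − 2.241) = 59.8% per test. Matching four tests to the four columns therefore does not by itself restore 80%.

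**The case against.** The best defence is that the SAP fits a separate regression for every outcome, so its success rule may mean only that each measure is judged on its own. Then 80% is right per measure before correction. This stands as a reading. It leaves the question-level gap open: the confirmatory claims are R2 and R3, and nothing turns two measure-level results into one answer.

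A second defence is that Bonferroni is planned, so the extra measures are paid for. This stands for false positives. A reader might infer from the bare p < .05 in the success rule that R2 and R3 each carry a false-positive rate of 8.0% to 9.75% (ρ from 0.7 to 0). The documents do not support that as the plan's error rate: it applies only if the either-one rule is used without the correction, and with it the rate stays below 5% per question. The defence does not rescue power, because Section 9.3 uses an uncorrected 0.05. The correction alone takes a single measure from 80.1% to 53.8% over six tests, a larger loss than the second measure causes, and it affects R1 and R4 as well.

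A reader might also take the rule to require success on all six measures at once, with uncorrected joint power of about 26% to 48% (ρ from 0 to 0.5). That is strained: the Protocol states four separate hypotheses, and nothing says that failure on one defeats the others.

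Finally, the size of the shortfall depends on unknown correlations and on equal effects. That is fair. At ρ = 0.9 the uncorrected figure for both measures, 75%, is not far below 80%.

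**Conclusion.** The mismatch is real and should be repaired, mainly as a missing decision rule. On the literal reading, where both measures must succeed, power for R2 or R3 is 64% to 75% for correlations of 0 to 0.9, against 80% stated. On the measure-by-measure reading, 80% holds per measure before correction, and the outcome of R2 or R3 is undefined when its measures disagree. Under the planned Bonferroni correction, power is 59.8% per test over four tests, or over six 53.8% per measure and 29% to 47% for both.

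These figures assume 310 analysed per arm, a true effect of 0.2 SD on both measures, one-tailed tests as in Section 9.3 and non-negative correlation; a negative correlation would lower the power for both further. The SAP does not restate the number of sides. Both R3 measures are limited to fathers who saw the child within the past month, so their sample may fall below 620, by an amount the documents do not give. The treatment-effect estimates themselves are unaffected.

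**What to change.** Before outcomes are compared by arm:

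1. Either name one deciding measure each for R2 and R3, with the other as a named secondary outcome, or keep both and state explicitly whether both or either must succeed. Which measure leads is the sponsor's choice. The multi-item averages cover more content, while fighting with the partner is arguably closer to the domestic-violence focus of the added curriculum.
2. Reword the SAP's success rule so that each of R1 to R4 is decided by its own stated rule.
3. State the Bonferroni family and the resulting alpha, and use that alpha in the success rule in place of the bare p < .05. This also requires settling whether parenting attitudes (R1) belong in the family: Protocol Section 1.2 calls them confirmatory and the SAP calls them secondary.
4. Restate the power in Section 9.3 under the chosen rule and corrected alpha.

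This is a change of wording and a recalculation; it needs no new data. The price is a stated power below 80% at the planned sample and, if lead measures are named, two of the six measures losing confirmatory status.
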